
Rigor of the prior research. There are noted gaps and weaknesses of the prior research that need to be addressed in order to move this field forward that this application plans to address. Historically, the consideration of pain impact has been overlooked, likely leading to inconsistent results among the literature observing the

relationship between AD/ADRD and chronic pain. Additionally, studies implicating lifestyle factors such as nutrition as a possible mechanism influencing the relationship between pain and cognitive disease have not been completed, despite evidence of nutrition status influencing on both disease states independently. Finally, the examination of epigenetics (influenced by nutrition) such as DNA methylation and epigenetic/cellular aging as a common mechanism driving both pain and AD/ADRD in tandem has not been appreciated. This proposal not only will provide the candidate with the opportunity to train in an outstanding research environment, but also allow her to contribute to filling the gaps in the literature that will allow the field to progress towards solutions to solve the complex problems seen in chronic pain and AD/ADRD.

5. Specific Aims

Specific Aim 1: Determine the association among DII, epigenetic clocks/cellular aging and cognitive function middle-age and older adults with low-impact pain, high-impact pain and pain free controls.

Hypotheses 1a-d: Individuals with chronic pain will (H1a) have a more positive/inflammatory DII, which will be associated with (H1b) accelerated epigenetic aging and (H1c) greater cognitive impairment. These associations will be more significant in the high-impact pain group compared to those with (H1d) low-impact pain and pain-free controls.

6. Research Plan

We propose a cross-sectional, observational study design that will assess the relationship between pain, cognition and dietary pattern in older adults with and without symptomatic knee OA pain. This will be completed in 2 experimental sessions approximately one week apart. After initial screening, eligible participants will undergo the sessions (health and sensory sessions) for collection of clinical, functional (physical, cognitive, emotional), QST, and blood-based biomarker data lasting 2-3 hours.

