Assessment of Adverse Events. A standard operating procedure will be established which is followed to collect and deal with adverse events during the research project. In particular, adverse events will be systematically monitored both during the sessions. In particular, participants will respond to a side effect check list to detect any possible physiological reactions related to the drug administration. This will include series of open-ended questions asked by trained research staff regarding any adverse events that have occurred since the last visit or phone contact. Open questions about pain experienced in various parts of the body will be delivered by study staff. Additionally, participants will be asked to the WOMAC and PANAS questionnaires to assess pain and feelings. This report will be reviewed by the principal investigator and study physician in a timely fashion. Any serious untoward event, whether related or unrelated to the study drug or procedures, will be reported to the UF IRB immediately as per their regulations.

Adverse events will be defined as any physical symptoms or side effects that began following session commencement. All reported and observed adverse events will be tracked in a running adverse events participant log, which will contain information regarding dates, description, and severity. All adverse events will be coded using the most current version of the Medical Dictionary for Regulatory

Activities (MedDRA). The number and percentage of participants reporting treatment-emergent adverse events will be tabulated by treatment, system organ class and MedDRA-preferred term. Treatment-emergent adverse events will be those adverse events that begin or worsened following the first dose of study drug. Adverse events will be further classified by severity and investigator-assigned relationship to the study variable. All reported and observed adverse events will be tracked on a running adverse events log (specific to each subject and maintained in his/her study file) and will contain information regarding onset/offset dates, time course (i.e., single, sporadic), severity, action taken regarding study drug, relationship to study drug, and whether it meets FDA criteria for "Serious." Each reported event is reviewed by the principal investigator and the study physician in a timely fashion. Additionally, the principal investigator reviews all adverse events recorded in each participant's log at the conclusion of study participation.

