In Case of Emergency. Participants will have 24-hour access to emergency care and will be provided with a means of contacting the on-call study doctor and research staff. Participants will be informed and encouraged to contact the study physician and study staff immediately with medical concerns or unusual reactions. Participants will also be informed of the closest Emergency Department location to their residence.

Data and Safety Monitoring Plan. A Data Safety Monitoring Plan will be in place. In particular, the following procedures will be implemented to ensure data and participant safety. Study progress and safety will be reviewed by the principal investigators in collaboration with [name], M.D., the study MD, and [name], M.D., Ph.D., the sponsor of the IND and consultant on the project. The Independent Safety Monitor for this study will consist of an established senior investigator not associated with our study. A study end report will be compiled and will include a list and summary of adverse events. In addition, this report will address: (1) whether adverse event rates are consistent with pre-study assumptions; (2) reason for dropouts from the study; (3) whether all participants met entry criteria; (4) whether continuation of the study is justified on the basis that additional data are needed to accomplish the stated aims of the study; and (5) conditions whereby the study might be terminated prematurely. The annual report will be signed by the Independent Safety Monitor and will be forwarded to the IRB, NIH, and FDA. The Data Safety Monitoring Plan will also require that all significant serious adverse events that may be possibly related to the study participation will be reported to the IRB, FDA, and NIH within 48 hours of the principal investigators learning of the event. In addition, any unanticipated serious adverse events that may increase the risk of the research for participants or potential participants will be reported to the IRB and the NIH within 48 hours of the principal investigators being informed about the event. This study will be stopped prior to its completion if: (1) the intervention is associated with adverse effects that significantly impact the risk-benefit ratio, (2) study recruitment or retention becomes futile, (3) any new information becomes available during the trial that necessitates stopping the trial; or (4) if independent safety monitor indicates stopping trial is necessary due to adverse event frequency or severity.

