ClinicalTrials.gov Requirements. In accordance with Public Law 110-85 and NIH guidelines, the proposed research will be registered with ClinicalTrials.gov prior to commencement of study procedures involving participants.

Blood Draw

The risks of drawing blood from a vein include discomfort at the site of puncture; possible bruising and swelling around the puncture site; rarely an infection; and, uncommonly, faintness from the procedure.

Blood Pressure Measurement

The risks of placing a blood pressure cuff on a participant's arms are that it may cause pinching or slight bruising.

Protocol: IRB201801467 (UCOPE Study)

IRB version: 10/1/2018

PI version: 05/10/2024

Physical Tests

There is a risk of losing balance and falling or development of chest discomfort due to coronary ischemia or dyspnea due to heart failure or lung disease associated with the physical performance-based testing (e.g., the ¼ mile walk test, balance tests, rising from a chair). We will minimize this risk by: (1) safely escorting participants to chairs located along the walking course should they become unsteady; (2) following participants at a close distance; and, (3) being at participants' side should they need assistance. Research staff members will be trained in the conduct of the physical performance tests before they work with study participants. Study staff members are trained not to perform these tests if they feel that testing is unsafe. In addition, participants will be asked whether they feel the test is safe. Those who state it may be unsafe will not be allowed to complete the test. Staff members will be trained to protect against falling and will be trained in CPR. They will be trained in activating the emergency response system at the research facility.

Sensory Testing

The sensory testing procedures may be uncomfortable or unpleasant, in that participants may experience some temporary discomfort from the thermal, pressure, and mechanical stimulation. However, if the participants feel the sensation is greater than they wish to tolerate, they can stop any of the procedures at any time.

Personal Information

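### PANDA's only specified adverse-event table is dated from a first drug dose and split by treatment, so it is empty by construction for the 40 new participants, who receive no drug

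*Combined protocol and SAP*

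**What the plan says.** PANDA section 6 (Research Plan) sets out the design: "We propose a cross-sectional, observational study design that will assess the relationship between pain, cognition and dietary pattern". It has two sessions about a week apart and no administration of oxytocin or placebo. Under Participants, it uses existing data and stored blood from 50 people and enrols 40 more who do not meet the parent study's eligibility criteria, for a total of 90.

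PANDA section 7, Assessment of Adverse Events, then gives these rules:

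- Base definition: "Adverse events will be defined as any physical symptoms or side effects that began following session commencement".
- Capture: "All reported and observed adverse events will be tracked in a running adverse events participant log". Events are MedDRA-coded, graded for severity and reviewed by the principal investigator and study physician.
- Tabulation: "The number and percentage of participants reporting treatment-emergent adverse events will be tabulated by treatment, system organ class and MedDRA-preferred term".
- Window for the tabulated events: "Treatment-emergent adverse events will be those adverse events that begin or worsened following the first dose of study drug".
- Relationship: one sentence asks for relationship to the study variable. The list of log fields asks for relationship to, and action taken with, the study drug.

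Under Sensory Testing, the same section says "participants may experience some temporary discomfort from the thermal, pressure, and mechanical stimulation". Under Data and Safety Monitoring Plan, the first stopping criterion is that "the intervention is associated with adverse effects that significantly impact the risk-benefit ratio".

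**The concern.** The tabulation rule and its window match the UCOPE text (UCOPE section 7, Assessment of Adverse Events), where a drug is given. For PANDA the base definition was moved from drug administration to session start, and one relationship phrase was changed. The window, the split by treatment and the drug-related log fields were left as they were. The section therefore has two anchors that do not agree, and the one governing the table refers to something that does not happen in PANDA.

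The harms that PANDA section 7 foresees come from procedures: falls or chest discomfort in the physical tests, faintness at blood draw, and discomfort from sensory testing. A table that cannot show such events for new participants invites a reader to take a structural zero for an observed one. The relationship fields do not help, because neither target is a procedure.

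Separately, the base definition covers any physical symptom after session start and says nothing about pain that the tests are designed to cause. Staff could reasonably log it or leave it out, and the overall event rate would then depend on that habit.

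**Working it through.** **Figures in the plan.** No adverse-event rate is stated for PANDA, so there is none to reproduce. The linked count adds up: 50 + 40 = 90.

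**Step 1: the table for the 40 new participants.** PANDA has no dosing step, and these participants fall outside the parent study's criteria, so I assume none was dosed there. An event enters the table only if it follows a first dose. The count is 0 of 40 for every true event rate. The usual exact 95% upper limit for 0 of 40, 1 − 0.025^(1/40) = 8.8%, has no meaning here, because the zero is not an observation.

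**Step 2: what a working table could show.** The documents give no expected rate, so the true share affected, p, is an assumption. The chance of at least one affected participant among 40 is 1 − (1 − p)^40:

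| Assumed p | Expected number affected | Chance of at least one | Chance under the present rule |
|---|---|---|---|
| 2% | 0.8 | 1 − 0.98^40 = 55% | 0% |
| 5% | 2 | 1 − 0.95^40 = 87% | 0% |
| 10% | 4 | 1 − 0.90^40 = 98.5% | 0% |

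**Step 3: the 50 with existing data.** The number of these dosed in UCOPE is not given. If their post-dose UCOPE events were counted, the table over all 90 could range from 0/90 = 0% to 50/90 = 55.6%. With 25 dosed and 30% of them affected (both assumed), it would be 25 × 0.30 / 90 = 8.3%. Such entries would be drug events of the parent trial and would say nothing about PANDA procedures.

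**Step 4: the base definition and test-evoked pain.** The pressure test ends when the participant first feels pain, and the conditioning stimulus is tuned to a rating of 40–60 out of 100 (PANDA section 6, Quantitative Sensory Testing). Let c be the share completing the pain tests, r the share of those whose evoked pain is logged as an adverse event, and q the rate of other events. Then

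any-event rate = 1 − (1 − c·r)(1 − q).

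With c = 0.95 and q = 0.10 (both assumed):

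- r = 0: 1 − 1 × 0.90 = 10%
- r = 0.25: 1 − 0.7625 × 0.90 = 31%
- r = 0.5: 1 − 0.525 × 0.90 = 53%
- r = 1: 1 − 0.05 × 0.90 = 95.5%

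The same underlying harm gives anything from 10% to 95.5%, depending on a logging choice that the plan does not state. This rate is not what the specified table reports. It would arise in an all-event summary.

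**The case against.** The strongest reply is that nothing is lost. Every reported or observed event goes into the log with its date, description and severity, and is coded and reviewed. The study-end report contains a list and summary not limited to treatment-emergent events. Serious events are reported whatever their relation to drug or procedures. A fall or a faint can therefore be found and told apart from test pain. A standard operating procedure for adverse events is also promised. It is not among the documents, and it may settle how evoked pain is recorded. On this view, one sentence was left over from the parent protocol and an editor can remove it.

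Most of that stands, and it rules out three stronger readings that a reader might infer:

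- *PANDA counts only post-dose events.* Only the table does. The log, the study-end list and serious-event reporting are wider.
- *The safety table must read 0% or 100%.* The 0% holds for new participants. The 100% comes from the base definition, which the table does not use, and it needs c = 1 and r = 1. The table is also split by organ class and preferred term, so test pain could not fill every row.
- *The monitor's stopping decision and the report item on event rates rest on this table.* The Data and Safety Monitoring Plan speaks of adverse-event frequency, severity and rates in general. It ties neither to the treatment-emergent table.

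What the reply leaves unanswered is that the only table the plan specifies does not work for the people PANDA enrols. Having the events in a log does not supply a rule for summarising them. The log's relationship field also asks about a drug that these participants do not receive.

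**Conclusion.** The point holds as a fault of tabulation and attribution. For the 40 new participants the specified table is structurally empty, 0 of 40. Any entries from the other 50 would be parent-trial drug events. This follows from the text, with the single assumption that none of the 40 was dosed in UCOPE. The 2%, 5% and 10% rates, and the values of c, r and q, are illustrations and not figures from the plan.

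The documents do not support a claim that harms go uncollected or that safety oversight is blind. No hypothesis, sample size, significance level or efficacy analysis is affected. The correction should still be made before PANDA events are summarised, because it is cheap and the present rule cannot be applied as written.

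**What to change.** In PANDA section 7, Assessment of Adverse Events:

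1. Tabulate adverse events that begin or worsen after session commencement, which is the anchor already in the base definition. Drop the first-dose window.
2. Split the table by pain-impact group (high-impact, low-impact, pain-free) instead of by treatment, keeping organ class and preferred term.
3. Replace relationship to study drug and to study variable with relationship to study procedures, in the text and in the log.
4. Record expected test-evoked pain separately from other adverse events, but keep in the adverse-event table any pain that leads a participant to stop a test or that persists after it. Excluding all evoked pain that resolves within the session would be too broad, since it would drop pain severe enough to end a test.

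In the PANDA Data and Safety Monitoring Plan, the first stopping criterion refers to an intervention that the study does not have. The two passages must be reconciled.

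The cost is protocol wording and one column on the log, with no new data collection.
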